6.2.2 The EGD examination procedure

The EGD examinations will be performed by experienced endoscopists using peroral conventional standard forward-viewing upper gastrointestinal video endoscopes at each center, within 48 hours of ds-MCE procedure. The endoscopist will not be blinded to the patient’s prior medical history but will be blinded to the preceding ds-MCE results. All procedures are conducted either without sedation or with sedation, according to the standard procedure of the center and the preference of the patient. During the course of the endoscopy, a complete evaluation of the esophagus, stomach and duodenum will be carried out. Grading of esophageal varices (when present) will be performed by all endoscopists using a predefined protocol: after examination of the stomach, the gastric cavity is fully deflated; the EGD is then withdrawn into the esophagus, and the esophageal lumen will be fully inflated. At that point, esophageal varices and red color signs will then be evaluated. The esophageal varices will be graded as small (<5 mm) or large (≥ 5 mm) and, if in doubt, it will be measured against the open endoscopic biopsy forceps (5 mm). The video of entire EGD examination procedure and the captured pictures will be digitally recorded for each participant.

“Procedural success of EGD” is defined as complete evaluation of the stomach and esophagus, irrespective of the completeness of duodenal evaluation. For patients who fail to complete esophageal and gastric evaluation under EGD, the reason will be documented in the case report form in time.

The coded videos and captured pictures of EGD examinations will be assessed by an independent imaging core-lab blinded to the patient identification information. Another two different independent gastroenterologists, who are experienced in EGD and are

blinded to the results of ds-MCE examinations, will analyse the recorded EGD images and videos. A consensus reading will be performed by a senior gastroenterologist experienced in ds-MCE in case of discrepancies. They will be instructed to identify and grade the esophageal varices (EV) and gastric varices (GV) according to the EGD grading system described in the “Study Outcomes Measurements” section, record the presence of portal hypertensive gastropathy (PHG). Besides, examination time of the whole EGD procedure will be recorded through the video and images. Other focal lesions observed in the esophagus, stomach and small bowel will also be recorded. All the results will be documented on the designated CRF.

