During the small bowel examination, the capsule moves passively under gastrointestinal peristalsis. After completion of the gastric examination, the operator then clicks the “small intestine mode” button under the “real-time view” interface. The capsule will be switched to “small intestine examination mode” with an adaptive capture rate of 0.5–6 fps. The capsule then moves passively under gastrointestinal peristalsis to further examine the small bowel. The patient will then be allowed to leave the hospital with the data recorder for further collection of images of the small intestine. Patients are allowed to drink clear water 2 hours after completing the gastric examination and a light meal 4 hours after completing the gastric examination. When the battery of capsule is exhausted or the capsule is discharged, the recording device and sensor array can be removed.

“Procedural success of ds-MCE” is defined as complete evaluation of the esophagus and stomach, irrespective of the completeness of small bowel evaluation. For patients who fail to complete esophageal and gastric evaluation under ds-MCE, the reason will be documented in the case report form in time.

(5) Collection of ds-MCE examination images

The patients will be instructed to return the data recorder after the capsule battery expired or the capsule is discharged. Then all images captured by the CE will be downloaded to the computer workstation by operator.

(6) Evaluation of ds-MCE examination

The coded videos of ds-MCE examinations will be assessed by an independent imaging core-lab blinded to the patient identification information. Two different independent gastroenterologists, who are experienced in MCE reporting and are blinded to the results of EGD examinations, will analyse the recorded ds-MCE images and videos. A consensus reading will be performed by a senior gastroenterologist experienced in ds-

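### Disputed EGD (reference standard) readings go to a senior reader described only by ds-MCE experience; the text does not require EGD experience or separation from ds-MCE adjudication, or name this reader in the blinding rules

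*Protocol*

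**What the plan says.** Protocol 6.2.2 sets up a core-lab reading of the EGD recordings: "The coded videos and captured pictures of EGD examinations will be assessed by an independent imaging core-lab blinded to the patient identification information". The two first-line readers are described as "Another two different independent gastroenterologists, who are experienced in EGD and are" blinded to the ds-MCE results. For disagreements the rule is: "A consensus reading will be performed by a senior gastroenterologist experienced in ds-MCE in case of discrepancies". The next sentence instructs the readers to grade esophageal and gastric varices "according to the EGD grading system", and the paragraph ends: "All the results will be documented on the designated CRF".

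The matching paragraph for the capsule, Protocol 6.2.1.2 item (6), uses the same sentence for its own adjudicator: "A consensus reading will be performed by a senior gastroenterologist experienced in" ds-MCE.

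SAP 5.5 lists four blinded roles: the ds-MCE operator, the EGD operator, the independent ds-MCE readers and the independent EGD readers. It does not mention a consensus reader for either test.

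**The concern.** EGD is the reference for the primary outcome and for every secondary accuracy outcome. A disputed EGD reading is by definition a hard case, and the consensus reader's call becomes the patient's reference status. Two things could go wrong.

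- **Knowledge of the index test.** If the reader knows or remembers the patient's capsule result, the EGD call can drift towards it. An index-test error then becomes agreement.
- **Less practice with EGD.** If the reader is less used to EGD images, the call can be wrong in either direction.

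The wording matters because it asks more of the two first-line EGD readers (EGD experience and stated blinding) than of the person who overrules them.

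**Working it through.** No figure in the plan is in dispute, so the check compares texts.

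**Step 1. What is required of each reader**

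| Requirement | First-line EGD readers | EGD consensus reader | ds-MCE consensus reader |
|---|---|---|---|
| Test-specific experience stated | EGD | ds-MCE | ds-MCE |
| Stated to differ from the readers of the other test | Yes (Protocol 6.2.2) | Not stated | Not stated |
| Named as blinded to the other test in Protocol 6.2 | Yes | Not named | Not named |
| Named in SAP 5.5 | Yes, item (4) | Not named; may fall under item (4) | Not named; may fall under item (3) |
| Coded recordings, core lab blinded to identity | Yes | Probably, as part of the core lab | Probably, as part of the core lab |

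**Step 2. Which disputes reach which outcome**

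The cells are those of SAP 7.3.7.1: a = both tests positive with matching location, b₁ = both positive with different location, b₂ = ds-MCE positive only, c = EGD positive only, d = both negative. Sensitivity is a/(a+b₁+c) and specificity is d/(b₂+d).

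- A dispute on whether varices are present can move a patient between c and d, or between b₂ and the EGD-positive cells.
- A dispute on location (esophagus or stomach) can move a patient between a and b₁.
- A dispute on size or red signs does not touch the primary outcome. It affects the large-EV reference that sets the circumference threshold, and the key secondary outcome, high-risk EV.

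**Step 3. Direction**

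If the reader follows the capsule, c becomes d and both measures rise. Likewise b₁ or b₂ becomes a, which raises sensitivity, and the b₂ change also raises specificity. If the reader's errors are unrelated to the capsule, correct agreements are turned into apparent errors. At the accuracy planned here, that lowers both measures. So the text does not fix even the sign of a possible bias.

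**Step 4. Size**

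The number of reference calls affected is (core-lab EGD disputes) × (share settled differently from how an EGD-experienced, blinded reader would settle them). The documents give neither term, so no expected bias can be calculated.

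**The case against.** The strongest reply is that this is an editing slip and the safeguards already exist.

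- **Carry-over.** The sentence repeats the capsule paragraph. The EGD paragraph also repeats that paragraph's line about small-bowel lesions, although the EGD examination is defined as esophagus, stomach and duodenum. This makes a copied sentence likely. It stands as an explanation, but the sentence is still the operative rule and needs correcting.
- **Blinding.** Someone who re-reads EGD recordings in the core lab is naturally one of the independent EGD readers of SAP 5.5 item (4), and the videos are coded. This largely stands, and the blinding part of the point is a request to make the rule explicit. Neither safeguard addresses EGD experience, and neither says that one person may not adjudicate both tests for the same patient.
- **Expertise.** Experience in ds-MCE does not exclude experience in EGD, the reader is senior, and the instruction to use the EGD grading system probably extends to this reader. That is fair: the text does not show a lack of EGD skill, only that none is required.
- **Unseen text.** The copy reviewed lacks some pages of both documents, apparently including Protocol 13.1 on study committees. Reader roles may be set out there. If so, 6.2.2 should be brought into line with them.

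A reader might infer more: that one person adjudicates both tests, or that the EGD adjudicator sees the capsule results. The documents say neither. They only fail to exclude the first, and SAP 5.5 item (4) probably excludes the second.

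**Conclusion.** The point holds as a wording and reading-order defect in the rule that settles the reference standard. It should be corrected, but it is not evidence of bias. It rests on two assumptions: that the core-lab EGD reading is the reference, which the text implies without saying so, and that the pages not seen do not already define the adjudicator.

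A reader might infer that a few adjudicated cases could decide the primary test. With 591 × 0.97 = 573 evaluable patients and 0.62 × 573 = 355 with EGV, the two-sided exact test against 85% needs 316 detected (p = 0.037; 315 gives p = 0.053). Results of 312 to 315 could therefore be turned by one to four favorable re-reads. The documents do not support treating this as the size of the problem. A result in that window has a probability of only about 15% at a true sensitivity of 90%, 25% at 88% and 5% at 85%. Even then, the re-reads would all have to go the same way, and nothing in the plan says how many disputes to expect or how they would be settled.

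**What to change.** 1. In Protocol 6.2.2, describe the EGD consensus reader as experienced in EGD and blinded to all ds-MCE images and results, in place of the ds-MCE experience.
2. In SAP 5.5, name the consensus readers in items (3) and (4).
3. Require that the EGD adjudicator has not adjudicated ds-MCE for the same patient. If one person must do both, EGD adjudication is completed and locked first, on videos coded separately from the capsule videos.
4. Report the number of EGD cases that went to adjudication.

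If reading is not finished, this costs a small constraint on reader assignment or reading order, with no added readers, patients or procedures. Recruitment was planned to January 2023 and the final SAP is dated 19 May 2023; the documents do not say whether reading was complete. If it was, new wording cannot change past calls. The remedy is then to disclose who adjudicated EGD and whether that reader was blinded, and to give the count in item 4.

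I would not add a re-analysis using the on-site endoscopist's result. It would change the reference for every patient and rely on a single reader who knows the medical history. It may also lack recorded data, and it could not isolate the effect of adjudication. Nor would I exclude adjudicated cases, since that removes the hard cases and tends to inflate accuracy even with a perfect adjudicator.

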6.3 Patient satisfaction assessment

After completing the ds-MCE procedure or EGD procedure, patients will undergo a face-to-face interview at which they are asked to respond to the questions on the three-item questionnaire that addressed procedure satisfaction.

(1) Did you experience discomfort during the ds-MCE/EGD procedure?

4 = none; 3 = minor; 2 = mild; 1 = severe; 0 = intolerable

(2) Did you experience discomfort after the ds-MCE/EGD procedure?

4 = none; 3 = minor; 2 = mild; 1 = severe; 0 = intolerable

(3) How would you rate the entire ds-MCE/EGD examination procedure?

4 = very comfortable; 3 = comfortable; 2 = tolerable; 1 = uncomfortable; 0 = very uncomfortable

6.4 Study follow-up

Two weeks following the ds-MCE procedure, patients will be contacted to confirm excretion of the capsule and to verify that there are no changes in their wellbeing following participation in this study. If the patient has not observed capsule excretion within 2 weeks, an X-ray procedure will be performed to confirm the capsule exit if deemed necessary by the investigator. This study is designed to comply with the requirements of good clinical practices and the other regulatory requirements that govern clinical research in China. During the study, adverse event and serious adverse event surveillance and reporting will be conducted accordingly.

6.5 Outcome measures

6.5.1 Primary outcome

The primary outcome is the sensitivity and specificity of ds-MCE to identify EGV in patients with cirrhosis, using the detection by EGD as the reference.

6.5.2 Secondary outcomes

6.5.2.1 Key secondary outcome

- i. The sensitivity, specificity of ds-MCE in detection of high-risk EV, using the detection by EGD as the reference.

The high-risk EV is identified by either large EV or small EV with presence of red signs according to the Baveno VI consensus¹.

6.5.2.2 Other secondary outcomes

- ii. The sensitivity, specificity, positive predictive value (PPV), negative predictive value (NPV) and overall diagnostic accuracy of ds-MCE in detection of high-risk EGV, using the detection by EGD as the reference.
High-risk EGV are defined as high-risk EV or any GV^{19,48}.
- iii. The sensitivity, specificity, PPV, NPV and overall diagnostic accuracy of ds-MCE in detection of EV, using the detection by EGD as the reference.
- iv. To investigate the optimal threshold of the proportion of ds-MCE esophageal luminal circumference occupied by the largest esophageal varix present in differentiating large EV from small or no EV, using the detection by EGD as the reference.
 - a) EV identified during EGD are classified based on the standard Baveno III consensus to differentiate between large EV (varix diameter $\geq 5\text{mm}$) and small EV (varix diameter $< 5\text{mm}$)⁴⁹.
 - b) As grading EV by endoscopy requires fully distention of the esophagus with air insufflation, which is lacking in CE, there has been no consensus on the standard classification of large EV under ds-MCE. In this study, we grade the EV under ds-MCE according to the proportion of the esophageal luminal circumference occupied by the largest esophageal varix present²⁶.
 - c) The Youden Index, defined as $[(\text{sensitivity} + \text{specificity}) - 1]$, will be calculated

to determine the optimal ds-MCE luminal circumference percentage threshold derived from the training cohort that resulted in the best combination of specificity and sensitivity for distinguishing large EV, using the results of EGD as the reference standard.

- v. The sensitivity, specificity, PPV, NPV and overall diagnostic accuracy of ds-MCE in detection of large EV, using the detection by EGD as the reference.
 - a) EV under EGD are classified into three grades: no, small or large, with the latter signifying a diameter ≥ 5 mm.
 - b) EV under ds-MCE are classified into three grades: no, small or large, with the latter signifying that the esophageal varix occupied more than the prespecified “optimal threshold” proportion of the capsule picture frame circumference.
- vi. The sensitivity, specificity, PPV, NPV and overall diagnostic accuracy of ds-MCE in detection of the red sign of EV, using the detection by EGD as the reference.
- vii. The sensitivity, specificity, PPV, NPV and overall diagnostic accuracy of ds-MCE in detection of gastric varices (GV), using the detection by EGD as the reference. GV are classified according to Sarin’s classification⁴. Gastric varices could be classified on the basis of its location in the stomach and its relationship with esophageal varices during ds-MCE procedure and EGD procedure. These are divided into two groups: gastroesophageal varices (GOV) and isolated gastric varices (IGV)^{4,46}. GOV1 are the extension of esophageal varices which across the cardia onto the lesser curve, and GOV2 extend onto the fundus. Isolated gastric varices (IGV) are vascular protrusions without direct connection to the esophageal varices. IGV1 are located in the fundus, while IGV2 are located elsewhere in the stomach, typically in the distal body and antrum.
- viii. The sensitivity, specificity, PPV, NPV and overall diagnostic accuracy of ds-MCE in detection of cardiofundal GV, using the detection by EGD as the reference. Cardiofundal gastric varices including GOV2 and IGV1 are at high risk of bleeding due to the unique vascular anatomy as opposed to lesser-curvature gastric varices (GOV1)⁵⁰.
- ix. The sensitivity, specificity, PPV, NPV and overall diagnostic accuracy of ds-MCE in detection of portal hypertensive gastropathy (PHG), using the detection by EGD as the reference.

The PHG is classified as four elementary gastric endoscopic signs proposed by the NIEC group: 1) mosaic like pattern (MLP); 2) red point lesions (RPL); 3) cherry

red spots (CRS); 4) black brown spots (BBS)^{3,51}.

- x. The incidence of PHE in small bowel under ds-MCE.

Endoscopic findings of PHE include mucosal inflammatory-like abnormalities, vascular lesions. In addition, mucosal inflammatory-like abnormalities and vascular lesions can lead to spontaneous bleeding⁵²⁻⁵⁴.

- xi. Examination time of ds-MCE and EGD procedures.

Examination time of ds-MCE include esophageal transit time (ETT), gastric examination time (GET), gastric transit time (GTT), small bowel transit time (SBTT), and total running time (TRT). ETT is defined as the time between the first esophageal image and the first gastric image. GET is defined as the time for examination of gastric primary anatomic landmarks twice. GTT is defined as the time between the first gastric image and the first duodenal image. SBTT is defined as the time between the first duodenal image and the first cecal image. TRT is defined as the time of the last picture taken by the capsule. Capsule endoscopy completion rate (CECR) is also recorded which defined as the proportion of the capsule that has a complete visualization of the entire small bowel⁴⁴. Examination time of EGD is defined as the duration from the endoscope entering to exiting from the esophagus.

- xii. Patient satisfaction score of ds-MCE and EGD procedures.

The patient satisfaction score assessment is based on the questionnaire of Section 6.3.

- xiii. Safety outcomes are based on adverse-event reporting.

All adverse events occurring during the study will be recorded.

7 Safety consideration

7.1 Adverse Events (AE)

Adverse events are defined as any undesirable experience occurring to a subject during the study, whether or not considered related to trial procedure. As far as possible, each AE should be evaluated to determine the severity grade (mild, moderate, severe); its relationship to the study procedure; its duration (start and end dates or if continuing at final exam); action taken (no action taken; hospitalization); whether it constitutes a serious adverse event (SAE). All adverse events reported spontaneously by the subject or observed by the investigator or his staff will be recorded and documented on the designated CRF.

7.2 Serious Adverse Events (SAE)

A Serious Adverse Event is any unfavorable event within the study timeframe fulfilling at least one of the following criteria:

- results in death;
- life-threatening (at the time of the event);
- inpatient hospitalization required or prolonged;
- event that results in persistent or significant disability/incapacity;
- medically important event or event that requires a medical or surgical intervention to prevent one of the above health implications.

Any other important medical event that did not result in any of the outcomes listed above due to interventions but could have been based upon appropriate medical judgment. An elective hospital admission will not be considered as a serious adverse event.

As far as possible, each SAE should be evaluated to determine the severity grade (mild, moderate, severe); its relationship to the study procedure; its duration (start and end dates or if continuing at final exam); action taken (no action taken; hospitalization).

Serious adverse events will be immediately, after coming to notice of the investigator, reported to the trial coordinator, who is 24/7 available. The investigator will report the following SAEs occurring in the study period to the sponsor without undue delay of obtaining knowledge of the events: death from any cause; esophagogastric variceal hemorrhage during ds-MCE examination; acute esophagogastric variceal hemorrhage

during EGD examination; acute esophagogastric variceal hemorrhage during ds-MCE examination. The investigator should report to the sponsor and ethics committee within 24 hours of SAEs. SAEs need to be documented additionally on a separate SAE form.

7.3 Follow-up of Adverse Events

All AEs will be followed until they have abated, or until a stable situation has been reached. Depending on the event, follow up may require additional tests or medical procedures as indicated, and/or referral to the general physician or a medical specialist. Assessment should be made at each visit (or more frequently, if necessary) of any changes in severity, the suspected relationship to the study, the interventions required to treat it and the outcome. For a follow-up report, the investigator may be required to collect further information for a detailed description and a final evaluation of the case, including copies of hospital reports and other relevant documents.

SAEs need to be reported till the end of the study in China, as defined in the protocol.

7.4 Monitoring of safety risks

For the monitoring of safety risks and potential harms for the study participants caused by study procedure or study design, the sponsor and a Data Safety Monitoring Board (DSMB) will carefully review all (S)AEs. In case of any safety issue that might change the risk benefit balance unfavorable, the sponsor will take appropriate measures to guarantee the safety of the patients.

8 Data handling and record keeping

8.1 Data collection

Source documents provide evidence of participant involvement, consent and permit collection of the data acquired. Data from source documents will be entered onto study CRFs. When the CRFs are complete, they will be reviewed and signed by the investigator and returned to the sponsor or designees. All data from the original CRF will be entered into a web-based electronic data capture (EDC) system by local research personnel. It allows the documentation of study data in electronic case report forms (eCRF). Subject records are coded by a unique study number. The local investigators

will keep a list showing codes and names. The EDC system includes password protection and internal quality checks to identify data that appear inconsistent, incomplete, or inaccurate. The technical support will be provided for the study centers during the study duration (administration of logins, roles and rights). The eCRF will be adapted due to changes in the study design, if necessary.

